**Investigational Agents:**

Drug Name:	E6 TCR
IND Number:	16078
Sponsor:	Center for Cancer Research
Manufacturer:	CC DTM

**Commercial Agents:** Interleukin-2

## **PRÉCIS**

### **Background:**

- Vulvar high-grade squamous intraepithelial lesion (HSIL) is a premalignant epithelial lesion that is frequently multifocal and/or recurrent.
- The primary treatment is surgery, which may result in disfigurement and compromise of the urethra, anus, or clitoris. Recurrence after surgery is common and primarily treated with additional surgery.
- Vulvar HSIL is caused by chronic infection with the human papillomavirus (HPV) type 16 infection. In this clinical trial the HPV-16 infection is targeted with a single infusion of autologous T cells that have been genetically engineered to express an HPV-16 E6-specific T cell receptor (E6 TCR T cells).

### **Objective:**

- Determine the safety of E6 TCR T cells for the treatment of vulvar HSIL.

### **Eligibility:**

- Histologically confirmed diagnosis of HPV-16+ vulvar HSIL.
- Expression of the HLA-A2\*02:01 allele.
- Measurable lesion(s) that are recurrent or cannot be resected with acceptable cosmetic or functional results.
- Age greater than or equal to 18 years old and less than or equal to 65 years old.
- Eastern Oncology Cooperative Group Performance Score of 0 or 1.

### **Design:**

- This is a phase I clinical trial with a 3+3 dose escalation design.
- Subjects will receive E6 TCR T cells followed by up to two doses of aldesleukin 720,000 IU/kg IV.
- No conditioning regimen will be given, aldesleukin will be capped at a maximum of two doses, and E6 TCR T cell dosing will begin at dose level -1 from the previously determined safe dose.

## **1. INTRODUCTION**

### **1.1 STUDY OBJECTIVES**

#### **Objectives:**

##### 1.1.1 Primary Objective

- Determine the safety of E6 TCR T cells for the treatment of vulvar HSIL.

##### 1.1.2 Secondary Objectives

- Assess clinical responses in subjects treated with E6 TCR T cells for vulvar HSIL.
- To evaluate a novel assay to genotype HPV from metastatic HPV+ cancers using a ddPCR-based blood test.

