### **1.2 BACKGROUND AND RATIONALE**

Vulvar high-grade squamous intraepithelial lesion (HSIL) is a premalignant condition that is caused by high-risk human papillomavirus (HPV) infection. The primary treatment for vulvar HSIL is surgical. Surgery can result in substantial morbidity, particularly for lesions that are multifocal, extensive, or adjacent to important anatomic structures (e.g. the anus, clitoris, or urethra). Following surgery, disease recurrence is common due to persistence of the underlying HPV infection. Therefore, a systemic treatment directed against the viral infection at the foundation of the disease may be more effective. This research protocol seeks to target the HPV infection that is causing vulvar HSIL with immunotherapy. The immunotherapy consists of autologous T cells that are genetically engineered to recognize the HPV-16 E6 oncoprotein, which is expressed by HPV-16 infected cells. The protocol is designed as a one-time treatment to clear the HPV infection and thereby cause regression of the HSIL lesions.

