## **2 ELIGIBILITY ASSESSMENT AND ENROLLMENT**

### **2.1 ELIGIBILITY CRITERIA**

#### **2.1.1 Inclusion Criteria**

- 2.1.1.1 Patients must have vulvar HSIL as confirmed by pathology report from a CLIA-certified laboratory.
- 2.1.1.2 Vulvar HSIL must be HPV-16+ by a PCR, RNA, or in situ hybridization test from a CLIA certified laboratory.
- 2.1.1.3 Patients must have measurable lesion(s) as defined in section 6.3.2 and one or more of the following criteria:
  - a. Failure of surgery to control disease (i.e. positive margins or recurrence of HSIL after surgery).
  - b. Multifocal or extensive disease for which surgery would result in major deformity that is not be acceptable to the patient.
  - c. Disease for which surgery would have a risk of functional impairment that is not be acceptable to the patient (i.e. involve partial or complete excision of the clitoris, anus, vagina, or urethra).
- 2.1.1.4 Patients may have received any previous therapy, including surgical excision, but must have histologically documented recurrence on new biopsy and a measurable lesion that meets the above criteria.
- 2.1.1.5 The presence of disease that can be biopsied for research purposes is not an inclusion criterion.
- 2.1.1.6 Patients must have the HLA-A\*02:01 allele

- 2.1.1.7 Age  $\geq 18$  years and  $\leq 65$  years. As age increases, the ability to tolerate the toxicities of aldesleukin decreases, so the patient population for this study will include up to and including 65 years of age to increase safety.
- 2.1.1.8 ECOG performance status of 0-1 as defined by **Appendix A**. Able to understand and sign the Informed Consent Document.
- 2.1.1.9 Women of child-bearing potential must have a negative pregnancy test. Women of child-bearing potential are defined as all women who are not post-menopausal or who have not had a hysterectomy. Postmenopausal will be defined as women over the age of 55 who have not had a menstrual period in at least 1 year.
- 2.1.1.10 The effects of E6TCR T Cells on the developing human fetus are unknown. For this reason, women of child-bearing potential must agree to use adequate contraception (hormonal or barrier method of birth control; abstinence) prior to study entry and for the duration of study participation. Should a woman become pregnant or suspect she is pregnant while she is participating in this study, she should inform her treating physician immediately.

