### 2.1.2 Exclusion Criteria

- 2.1.2.1 Patients who are receiving any other investigational agents
- 2.1.2.2 Because there is an unknown but potential risk for adverse events in nursing infants secondary to treatment of the mother with E6 TCR, breastfeeding should be discontinued if the mother is treated with E6 TCR. These potential risks may also apply to other agents used in this study.
- 2.1.2.3 Uncontrolled intercurrent illness including, but not limited to, any ongoing or active infection (e.g. requiring anti-infective therapy), coagulation disorders, cardiovascular disorders, respiratory disorders, cancer, or psychiatric illness/social situations (within the last six months) that would limit compliance with study requirements.
- 2.1.2.4 Any form of systemic immunodeficiency, including acquired deficiency such as HIV or primary immunodeficiency such as Severe Combined Immunodeficiency Disease. The experimental treatment being evaluated in this protocol depends on an intact immune system. Patients who have decreased immune competence may be less responsive to the treatment.
- 2.1.2.5 Concurrent systemic steroid therapy if greater than the equivalent of 5 mg prednisone PO daily. Patients previously on steroids must be off steroids for four weeks prior to treatment.
- 2.1.2.6 Any history of clinically significant cardiac arrhythmia, coronary revascularization, ischemic symptoms, or previously documented LVEF of less than or equal to 45%. A cardiac stress test is required for all patients greater than 50 years old. A cardiac stress test may also be performed for any clinical concern. Patients with cardiac ischemia are not eligible.
- 2.1.2.7 Patients with any active invasive cancer are not eligible.
- 2.1.2.8 Patients vulvar HSIL that is not HPV-16+ or is associated with multiple types of high-risk HPV are not eligible.

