## **2.3 REGISTRATION PROCEDURES**

Registration will be a two-part process as patients are screened on this protocol. Authorized staff must register an eligible candidate with NCI Central Registration Office (CRO) within 24 hours of signing consent. To initially register a subject after the participant has signed the consent, complete the top portion of the registration Eligibility Checklist from the website (<http://home.ccr.cancer.gov/intra/eligibility/welcome.htm>) indicating that the patient is being registered for screening and send via encrypted email to: NCI Central Registration Office [[contact]](mailto:[contact]). Once eligibility is confirmed after completion of screening studies, complete the remainder of the form which is the eligibility checklist, indicating that the patient is being registered for treatment and email the completed registration checklist to the CRO at NCI Central Registration Office [[contact]](mailto:[contact]). After confirmation of eligibility at Central Registration Office, CRO staff will call pharmacy to advise them of the acceptance of the patient on the protocol prior to the release of any investigational agents. Verification of Registration will be forwarded electronically via e-mail to the research team. A recorder is available during non-working hours.

Subjects that do not meet screening criteria should be removed from the study following the procedure in section **3.6.3**.

2.3.1 Treatment Assignment and Randomization/Stratification Procedures for registration purposes only

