#### **5.1.1 Pre cell infusion evaluations**

- The following samples will be drawn for research and sent to the ETIB preclinical core within 4 weeks prior to cell infusion. Send to [name], Pre-Clinical Core lab; Attention [name], [name] contact [contact].
  - 6 CPT tubes (8mL each). One CPT tube per time point will be used to collect 4mL of plasma, which will be frozen in 4mL vials. PBMC from the remainder of the CPT tubes will be frozen in aliquots of 10 x 10^6 cells/vial
  - 1 SST tube (8mL) for sera. Serum will be processed in the ETIB Pre-Clinical Core and aliquoted into vials of 0.5-1 mL each.
- During screening, one 10 mL tube of blood will be collected from each patient in a Cell-Free DNA BCT tube. Specimens may be drawn at the patient's local doctor's office or laboratory and FedExed to the assigned research nurse. Specimens will be transported by the assigned research nurse to [name] lab for sample labeling. Contact [name], [name]. HPV-16 in peripheral blood via ddpCR assay samples will be coded with a patient identification number, and linked to samples by that identification number in LabMatrix. Access to personally identifiable information (PII) is

limited to the PI and study personnel who interact directly with the patient and their samples. Once labeled, samples will be sent to the laboratory of [name], Genetics Branch, CCR for HPV-16 ddpCR assay testing. See **Appendix E** for collection and processing instructions, which will be sent to the patient.

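### Secondary objective 1.1.2 is set in metastatic HPV+ cancers, which this vulvar HSIL trial does not enrol, and eligible patients alone cannot show the HPV-16 assay's false positives or whether it separates types

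*Combined protocol and SAP*

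**What the plan says.** The second secondary objective in Section 1.1.2 reads: "To evaluate a novel assay to genotype HPV from metastatic HPV+ cancers using a ddPCR-based blood test".

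The rest of the document describes a different population:

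- Section 1.2: "Vulvar high-grade squamous intraepithelial lesion (HSIL) is a premalignant condition".
- Section 2.1.1.2: "Vulvar HSIL must be HPV-16+ by a PCR, RNA, or in situ hybridization test from a CLIA certified laboratory".
- Section 2.1.2.7: "Patients with any active invasive cancer are not eligible".
- Section 2.1.2.8: "Patients vulvar HSIL that is not HPV-16+ or is associated with multiple types of high-risk HPV are not eligible".
- Section 2.3.1 defines both cohorts as HPV-16-positive vulvar HSIL.

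On sampling, Section 5.1.1 says: "During screening, one 10 mL tube of blood will be collected from each patient in a Cell-Free DNA BCT tube". Section 2.2.1, item f, lists the same tube as being for an optional research test. Section 5.1.1 sends the sample to the "Genetics Branch, CCR for HPV-16 ddpCR assay testing", and the title of Appendix E also names HPV-16. No other type and no panel is mentioned for this test.

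On who is on study at that stage, Section 2.3 says: "Registration will be a two-part process as patients are screened on this protocol". Section 8 allows up to 200 enrolments, a ceiling that covers screen failures and non-evaluable patients.

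Section 6.3.1 defines evaluability for toxicity and for response only. Section 8 restates the secondary objectives as clinical response plus exploratory translational analyses. It does not name the assay, the patients in whom it will be evaluated, or the comparator.

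**The concern.** A secondary objective should name a population that the trial can supply and a quantity that its data can estimate. This one names a population that the eligibility criteria rule out, and an aim (genotyping) that goes beyond the single type named wherever the test is described.

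The eligibility filter then matters for analysis. Treated patients are selected to be positive for the type that the assay detects, and to have no other high-risk type in the lesion. If the assay were summarised only in them, the report could show how often HPV-16 is found in blood when the lesion is positive. It could say nothing about how often blood is positive when the lesion is not. Nothing in Section 8 prevents that choice of analysis set.

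**Working it through.** The plan gives no sample size, accuracy target or interval for this assay, so there is no figure to reproduce. The check compares sections and then does one short calculation.

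**Step 1: population.** The objective requires metastatic HPV+ cancer. Both cohorts in Section 2.3.1 are vulvar HSIL, Section 1.2 calls that disease premalignant, and 2.1.2.7 excludes active invasive cancer. No section provides for enrolling metastatic disease. Eligible patients who match the objective as worded: 0.

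**Step 2: type.** The objective says genotype. Section 5.1.1 and Appendix E describe an HPV-16 ddPCR test. One named type supports detection of that type; it does not by itself support assignment among types.

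**Step 3: what eligible patients can show.** Take the vulvar lesion's tissue result as the reference.

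- Criterion 2.1.1.2 requires the lesion to be HPV-16-positive, so eligible patients with an HPV-16-negative lesion number 0. Negative agreement (the complement of the false-positive rate) has denominator 0.
- Criterion 2.1.2.8 also removes lesions with multiple high-risk types, so eligible patients whose lesion carries another high-risk type number 0. Type discrimination has denominator 0.
- Positive agreement can be estimated.

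**Step 4: who could fill the gap.** Screening takes place on this protocol after consent (Section 2.3), the tube is a screening sample (Sections 2.2.1, 5.1.1 and 5.2), and Section 8 counts screen failures within enrolment. Patients found to have HPV-16-negative lesions can therefore have a blood sample. How many will have both a tube and a tissue HPV result is not in the documents.

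**Step 5: how many would be needed.** If all n HPV-16-negative patients are also blood-negative, the exact (Clopper-Pearson) two-sided 95% lower limit is L = 0.025^(1/n). So n must be at least ln(0.025)/ln(L), with ln(0.025) = -3.689.

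| Lower limit wanted | Calculation | Smallest n | Limit at that n |
|---|---|---|---|
| 80% | 3.689 / 0.2231 = 16.5 | 17 | 0.805 |
| 90% | 3.689 / 0.10536 = 35.01 | 36 | 0.903 |
| 95% | 3.689 / 0.05129 = 71.9 | 72 | 0.950 |

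These are best cases. Any disagreement raises the number needed.

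**Step 6: who is sampled.** Section 2.2.1 makes the test optional, while Section 5.1.1 has the tube drawn from every patient. The expected number of tubes depends on which applies.

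**The case against.** The sponsor could reply as follows.

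- **The phrase describes the assay's origin, not the trial's patients.** This is possible. But the objective then names no population in this trial, so it needs correcting on either reading.
- **HPV-16 is named.** This stands. A reader might infer that the document never says which type is tested; Section 5.1.1 and Appendix E rule that out. What remains is the mismatch between a test described for one type and an aim to genotype.
- **The exploratory translational analyses in Section 8 cover it.** They could cover a descriptive summary. They do not say in whom or against what, and Step 3 shows that the choice of patients decides what can be learned.
- **Optional and every patient can be reconciled** if the latter means every patient who agrees. That is plausible, but the document should say so.
- **Blood against the vulvar lesion is an imperfect comparison.** This stands. Section 2.2.1 includes cervical high-risk HPV testing, and Section 3.5.2 repeats it when the screening result was HPV-16-positive. The protocol therefore allows for HPV-16 at another site. A patient with an HPV-16-negative vulvar lesion and HPV-16 at the cervix could be blood-positive without any assay error. The tissue method also varies (PCR, RNA or in situ hybridization). For these reasons agreement is a safer term than sensitivity and specificity.
- **No accuracy target or decision rests on the test.** This is correct, and it is why the point is minor.

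**Conclusion.** The concern holds as a minor one. The objective cannot be answered as worded, and two denominators among eligible patients are 0: patients with metastatic HPV+ cancer, and patients whose lesion is HPV-16-negative or carries another high-risk type. The second zero assumes that the lesion's tissue result is the reference and that the eligibility criteria are applied as written. The figures of 17, 36 and 72 assume complete agreement.

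Two stronger readings are tempting and are not supported. One is that false positives cannot be studied on this protocol at all; the screening tubes of patients with HPV-16-negative lesions could supply them. The other is that the ceiling of 200 indicates how precise the result would be. That ceiling is not a forecast of paired blood and tissue results, and the documents give no proportion of HPV-16-negative patients and no expected error rate.

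The primary safety objective is unaffected, and no dose, stopping or enrolment decision depends on this test.

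**What to change.** - **Section 1.1.2:** replace the metastatic-cancer population with patients screened for vulvar HSIL. Call the aim HPV-16 detection unless the assay reports other types, in which case list them.
- **Section 8, analysis set:** name it as all consented screened patients with both a blood tube and an available tissue HPV result, including HPV-16-negative screen failures.
- **Section 8, reporting:** give positive and negative agreement with the tissue result, each with an exact 95% confidence interval. List the tissue method for each patient, and the cervical HPV result where there is one, so that HPV-16 at another site is not counted as an assay error. Count the patients who lack either the blood or the tissue result.
- **Sections 2.2.1 and 5.1.1:** reconcile whether the tube is optional or drawn from every patient.

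The cost is wording, plus keeping the tissue HPV result and its method for screen failures where one exists. No new procedure or patient is needed. The downside is that a tissue HPV result is not assured for every screen failure, so the HPV-16-negative group may be small and its interval wide.

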##### 1.1.3 Exploratory Objectives

- Test for clearance of HPV infection from vulvar tissues.
- Evaluate the expansion, survival, trafficking, phenotype, and function of E6 TCR cells following infusion.
- Investigate the vulvar HSIL microenvironment including immune cell subsets and costimulatory/inhibitory molecules.
- Assess circulating HPV DNA levels associated with treatment.

### **1.2 BACKGROUND AND RATIONALE**

Vulvar high-grade squamous intraepithelial lesion (HSIL) is a premalignant condition that is caused by high-risk human papillomavirus (HPV) infection. The primary treatment for vulvar HSIL is surgical. Surgery can result in substantial morbidity, particularly for lesions that are multifocal, extensive, or adjacent to important anatomic structures (e.g. the anus, clitoris, or urethra). Following surgery, disease recurrence is common due to persistence of the underlying HPV infection. Therefore, a systemic treatment directed against the viral infection at the foundation of the disease may be more effective. This research protocol seeks to target the HPV infection that is causing vulvar HSIL with immunotherapy. The immunotherapy consists of autologous T cells that are genetically engineered to recognize the HPV-16 E6 oncoprotein, which is expressed by HPV-16 infected cells. The protocol is designed as a one-time treatment to clear the HPV infection and thereby cause regression of the HSIL lesions.

#### 1.2.1 Vulvar high-grade squamous intraepithelial lesion (HSIL)

Vulvar HSIL is defined by the 2015 International Society for the Study of Vulvovaginal Disease (ISSVD) as an HPV-associated lesion of the vulva that has high malignancy potential. The term, vulvar HSIL, is equivalent to the previously used nomenclature of vulvar intraepithelial neoplasia, usual type [1]. It does not include low-grade squamous intraepithelial lesions without malignant potential such as condyloma acuminatum. It also does not include premalignant lesions that are not associated with HPV, which are classified as differentiated-type vulvar intraepithelial neoplasia. Multiple HPV types can cause vulvar HSIL but HPV-16 is the most prevalent [2]. Spontaneous regression of vulvar HSIL is rare, reportedly occurring in fewer than 1.5% of patients per year [3].

Patients with vulvar HSIL may present with symptoms of local itching, burning, or pain. Diagnosis is suggested by careful inspection of the lesion(s) and is confirmed by biopsy. Multicentric disease is common due to diffuse spread of HPV infection throughout vulvar epithelium. Vulvar HSIL transforms into vulvar squamous cell carcinoma (SCC) in 3 to 9% of patients. Therefore, all lesions require surveillance with physical exams and biopsies to rule out invasive cancer [4]. For lesions that do not regress, excision is required. The type of surgery depends on the extent and anatomic location of disease. Treatment of multifocal lesions, extensive disease, or lesions in proximity to the urethra, clitoris, or anus can result in deformity and functional impairment. Even with radical excision to negative margins, recurrence occurs in approximately 30% of patients [5]. Thus, surgery may be an unsatisfactory treatment option as it often fails to prevent disease recurrence, results in morbidity, and negatively impact psychological and sexual health [6].

### 1.2.2 Studies of the natural history and treatment history of vulvar HSIL

Studies of the natural history and treatment of vulvar HSIL are scientifically limited as they are mostly retrospective and have small sample sizes. One systematic review reported that 6.5% of 3322 patients with vulvar HSIL progressed to develop an invasive vulvar carcinoma [3]. In untreated patients, invasive vulvar carcinoma developed in nine percent of subjects within one to eight years. Invasive cancers are treated with radical local excision or modified radical vulvectomy, depending on the tumor stage. Locally advanced cancers are treated with chemoradiation. Salvage surgery with pelvic exenteration and colostomy or ureteral diversion may be employed. Five-year survival for local, regional, and distant vulvar cancers are 86%, 54%, and 16% respectively. A study based on data from the United States reported the incidence of vulvar HSIL to be 2.86. per 100,000 women [7]. Immunotherapy for vulvar HSIL

Vulvar HSIL is caused by HPV infection, and HPV infections can be recognized and attacked by the immune system. Hence, immunotherapy is an attractive treatment strategy for vulvar HSIL. Topical immunotherapy with imiquimod, an immune response modifier that activates dermal dendritic cells through Toll-like receptor 7, has been reported to have response rates of 13-81%, but vulvar inflammation and pain limit its use and it is not currently FDA-approved [8]. Nonetheless, it is a treatment option that some patients should consider as an alternative to this protocol. Experimental vaccines have been tested for the treatment of vulvar HSIL. A clinical trial of a vaccine targeting HPV-16 E6 and E7 showed promising results in a single-arm phase II study [9]. This vaccine is experimental and not available outside of a clinical trial. The preventative vaccines for HPV (e.g. Gardasil and Cervarix) are highly effective at preventing HPV infections but not considered effective for the treatment of VIN [10].

[figure not shown]
